3.2.2.1.2 Study periods for efficacy data

The following study periods are defined for the classification of efficacy data by study period:

- **Screening Period:** Starts at the time of the informed consent date and ends prior to the day and time of the first IMP administration.
- **16-Week Double-Blind Treatment Period:** Starts on the day of the first IMP administration and ends the day of the Week 16 Visit or on the day of the ET Visit for study participants withdrawn from the study before Week 16 visit. If Week 16 Visit is missing or skipped, the DBTP will end on the day of the last visit before Week 16.

Efficacy assessments from the Week 16 Visit belong to the DBTP as they are conducted prior to the Week 16 IMP administration.

- **36-Week Maintenance Treatment Period:** Starts on the day after the Week 16 Visit and ends the day of Week 52 Visit. If the Week 16 Visit is missing, the MP will start the day after the date of the last visit before Week 16. For study participants withdrawn from the study after Week 16 but before Week 52, the MP will end at the ET Visit.

A study participant will be considered to have completed a study period if they complete the last planned study visit for that period.

It is possible for a study participant to discontinue the study after completing the Week 16 efficacy assessments, (and therefore after completing the DBTP), but prior to entering the MP the next day. Therefore, all study participants who discontinue at or after Week 16 and never start the MP will be counted as having discontinued in the overall period only.

3.2.2.2 Coronavirus Disease 2019 (COVID-19) pandemic periods

The following COVID-19 pandemic periods will be defined:

- Prior COVID-19 pandemic period: Period prior to COVID-19 pandemic start date, which is defined as 11-Mar-2020 by the World Health organization (WHO), not including the pandemic start date.
- COVID-19 pandemic period: Period from 11-Mar-2020 through the COVID-19 pandemic end date (which is currently not defined), including the dates of pandemic start and end.
- Post COVID-19 pandemic period: Period after the WHO declaration of the end of the pandemic, beginning on the day after the pandemic end date. The end of the pandemic had not yet been declared at the time of SAP finalization. As a result, this period will only be included in analyses if the WHO declares an end to the pandemic prior to the end of the study.

These periods will be used to classify the timing of the following relative to COVID-19 pandemic:

- study participant enrolment in the study,
- study participant Week 16 Visit,
- AE onset date.

3.2.3 Mapping of assessments performed at Early Termination Visit

If the early termination visit occurs at a scheduled visit as outlined in the schedule of assessments, then no mapping is necessary, and any early withdrawal assessments should correspond to that scheduled visit. Premature study termination visit assessments that occur on a date after a scheduled visit will be assigned to the next scheduled site visit per the protocol following the last visit where assessments were available. The only exception to the above rule is for anti-bimekizumab antibody assessments, in which all early withdrawal visit assessments will be assigned to the next scheduled visit at which anti-bimekizumab antibodies are assessed.

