3.4 Treatment Discontinuation Date and Intercurrent Event Date

The concept of intercurrent event is one of the estimand attributes as defined in Section 8.1.2 and Section 8.1.3. For non-responder imputation (NRI) analyses of binary efficacy endpoints, the intercurrent event date will be defined as the date of treatment discontinuation due to any reason. For multiple imputation (MI) analyses of binary efficacy endpoints, the intercurrent event date will be defined as the date of treatment discontinuation due to AE (including death) or lack of efficacy, while for the multiple imputation analyses of continuous and categorical efficacy endpoints (including the reference-based and hypothetical MI analyses), the intercurrent date will be defined as the date of treatment discontinuation due to any reason. Since treatment discontinuation date is not collected, the treatment discontinuation date is defined as:

Treatment end date + dosing interval (28 days) + visit window (3 days for DBTP, 4 days for the MP)

With “Treatment end date” derived from the “Study Medication Discontinuation” CRF.

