4.2.1.3 Composite Estimand - Non-Responder Imputation (NRI) analysis

This is the primary analysis for the ASAS40 primary efficacy endpoint.

In the NRI analysis, study participants will be classified as ‘non-responders’ (ie, as if they have not responded to the treatment) at all time points after the date of discontinuation of study treatment for any reason.

In addition, for all endpoints except the ASAS response for which the response is still calculable when there is only 1 component with missing data (see Section 4.2.1.1), study participants will also be classified as ‘non-responders’ at all timepoints they had missing data.

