4.2.1.4.1 Non-composite binary endpoints (Modified Composite Estimand)

For non-composite binary endpoints, the MI method will be applied as follows based on raw values:

- Step 1: Any observation after date of discontinuation of study treatment for any reason will be set to missing.
- Step 2: Create a dataset, one for each treatment group, of study participants with observed values and those needing estimation by multiple imputation. For the imputation step, missing values will include non-monotone missing values (ie, intermittent missing values between completed assessments) and monotone missing values (ie, where all study participant data is missing after a given time point).
 - **Step 2a:** First, the intermittent missing values in each dataset will be imputed using the MCMC method with multiple chains, monotone missing data imputing pattern, and non-informative priors for all parameters. Unless specified differently, the first 200 iterations will not be used (the ‘burn-in’ option). A total of 100 sets of imputations will be

performed. The seed used for these imputations will be 2017 and all other multiple imputation procedures described in this SAP will use this same seed as well.

- **Step 2b:** If an imputed value falls outside of the pre-defined range of values for the given variable, the value will be truncated to be within the predefined range of values for the endpoint of interest. For example, the imputed value for BASDAI will be updated to 0 or 10 in the case of an imputed value less than 0 or greater than 10, respectively (see [Table 4–2](#)).

The resulting 100 imputed data sets will have a monotone missing data pattern and will be imputed using a method for monotone missingness:

- **Step 2c:** For monotone missing data, monotone regression will be used to impute missing data. A separate regression model is estimated for each variable with missing values (ie, measurement at each time point). Based on the resulting model, a new regression model is then drawn and is used to impute the missing values for the variable. Since the data set has a monotone missing data pattern, the process is repeated sequentially for variables with missing values. The procedure will be based on the 100 imputed datasets generated from the MCMC procedure and will be performed by Imputation.

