4.2.1.4.2 Composite binary Endpoint (Modified Composite Estimand)

For composite binary endpoints, the MCMC/monotone regression method described above in Steps 1 to 3 for handling intermittent and monotone missing data will be performed separately for each individual component variable. As mentioned above, study participants with missing

Baseline will also be included in the imputation step. Refer to Section 4.2.1.1 for details on the handling of missing and zero Baseline for ASAS endpoints.

Then, based on the multiply imputed data sets obtained for each component, the binary response will be derived as follows:

- The 100 data sets obtained for each component will be merged by imputation number and study participant number.
- For each of the 100 complete imputed data sets, the binary endpoint will be derived for each study participant/visit based on the component values. In the case of the ASAS40 and ASAS20 where only one component value (among the 4) is missing at a visit, the response will be derived without using the imputed value of the missing component.
- If study participants have a treatment discontinuation due to AE or lack of efficacy, then the response associated to the binary endpoint will be changed to “non-response” for all visits after the IE date.

Procedures described for Step 4 to Step 5 will then follow.

For the primary endpoint, the ‘burn-in’ option in PROC MI will be set to the default value (200 in this case). The convergence of the MCMC will be assessed graphically, and the results will be provided in a SAS® output.

In addition, for ASDAS-MI endpoint, the following actions should also be taken:

- in step 2b and 2d, any imputed CRP values $<0.5 * \text{the LLOQ (0.1)}$ will be reset to 0.05 after each MCMC and monotone steps to account for potentially different LLOQs across individuals,
- when determining ASDAS-MI, ASDAS-CRP values <2 should be reset to 2 only after the monotone regression imputation step (i.e., after Step 2d) prior to calculation of the composite score.

4.2.1.5 Calculation of adjusted responder rates, odds ratio and CIs for binary endpoints.

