8.1.2 Primary analysis of the primary efficacy variable

The primary efficacy variable (ASAS40 response at Week 16) will be analyzed for all study participants in the RS.

The primary efficacy analysis will evaluate the composite estimand (NRI) that combines the clinically meaningful improvement from Baseline in ASAS40 response at Week 16 and the intercurrent event of not discontinuing early from study treatment for any reason prior to Week 16.

Note that only **permanent** discontinuations are considered as intercurrent events. This definition is applicable to all analyses defined in this SAP.

The following 4 attributes describe the composite estimand that will be used to define the treatment effect of interest for the primary efficacy analysis:

- Population = Study participants enrolled according to the protocol-specified inclusion/exclusion criteria and randomized to IMP
- Study participant-level outcome = ASAS40 at Week 16
- Intercurrent event handling = An intercurrent event is defined as discontinuation of study treatment prior to Week 16. A composite strategy will be implemented in which a positive clinical outcome is defined as achieving ASAS40 at Week 16 and not discontinuing study treatment through Week 16.
- Population-level summary measure = Conditional odds ratio comparing bimekizumab to placebo.

Intercurrent events will then be acknowledged as an unfavorable outcome for the composite estimand in considering study participants with intercurrent events as ‘non-responders’ to the study treatment.

Consequently, if the date of an intercurrent event (as defined in Section 3.4) occurred prior to or at Week 16, study participants will be considered as “non-responders” at Week 16.

Additionally, missing data at Week 16 that are not preceded by an intercurrent event will be imputed as non-responders.

As outlined in Section 4.5, the statistical null hypothesis for the ASAS40 response at Week 16 is that there is no difference in the proportion of study participants with ASAS40 response between the bimekizumab treatment and placebo (ie, the conditional odds ratio for ASAS40 response in the bimekizumab treatment compared with placebo is equal to 1). The alternative hypothesis is that there is a difference between bimekizumab treatment and placebo.

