8.1.4.4 Analysis using modified composite estimand - MI

A supportive analysis will evaluate the modified composite estimand (Section 4.2.1.4.2) that combines the clinically meaningful improvement from Baseline in ASAS40 response at Week 16 and the intercurrent event of not discontinuing early from study treatment due to AE or lack of efficacy prior to Week 16.

The same logistic regression model as the one used for the primary efficacy analysis will be used on the RS. The following 4 attributes describe the estimand that will be used to define the treatment effect of interest for this analysis:

- Population = Study participants enrolled according to the protocol-specified inclusion/exclusion criteria and randomized to IMP
- Study participant-level outcome = ASAS40 at Week 16
- Intercurrent event handling = An intercurrent event is defined as discontinuation of study treatment due to AE (including death) or lack of efficacy, prior to Week 16. A composite strategy will be implemented in which a positive clinical outcome is defined as achieving ASAS40 at Week 16 and not discontinuing study treatment due to AE or lack of efficacy through Week 16.
- Population-level summary measure = Conditional odds ratio comparing bimekizumab to placebo.

Intercurrent events (Section 3.4) will be acknowledged as an unfavorable outcome for this modified composite estimand in considering study participants with intercurrent events as ‘non-responders’ to the study treatment.

Missing data at Week 16 that are not preceded by an intercurrent event will be imputed by standard MI techniques. Refer to Section 4.2.1.2 for further details.

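### Section 3.2.3 puts no day limit on mapping early-termination efficacy assessments, so a value taken up to about four weeks early can serve as Week 16, and the date that stands for Week 16 is undefined

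*SAP*

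**What the plan says.** **Mapping.** Section 3.2.3 covers early-termination (ET) visits that do not coincide with a scheduled visit: "Premature study termination visit assessments that occur on a date after a scheduled visit will be assigned to the next scheduled site visit". The next visit is counted from the last one with assessments. There is no earliest or latest day, and anti-bimekizumab antibody data are the only exception. The BASMI derivation in Section 8.2.1.7 (step 5) applies the rule to an efficacy score.

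**Scheduled-visit rule.** Section 3.1 restricts the analysis to data from scheduled visits, with exceptions only for PK, some vendor data and MRI. ET data are not among them. The same section gives the protocol visit window of ±3 days through Week 16.

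**Event date.** Section 3.4 defines treatment discontinuation as "Treatment end date + dosing interval (28 days) + visit window (3 days for DBTP, 4 days for the MP"), with the treatment end date taken from the Study Medication Discontinuation CRF.

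**Non-response.** Section 8.1.2 imposes it "if the date of an intercurrent event (as defined in Section 3.4) occurred prior to or at Week 16". Section 4.2.1.3 imposes it "at all time points after the date of discontinuation of study treatment for any reason". The estimand in Section 8.1.2 reads: "a positive clinical outcome is defined as achieving ASAS40 at Week 16 and not discontinuing study treatment through Week 16". The modified composite estimand (Section 8.1.4.4) has the parallel condition "not discontinuing study treatment due to AE or lack of efficacy through Week 16". Its imputation steps (Section 4.2.1.4) are also tied to the event date: "Any observation after date of discontinuation of study treatment for any reason will be set to missing", and non-response is imposed "for all visits after the IE date".

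**The concern.** Week 12 is the last visit before Week 16, so any ET assessment made after an attended Week 12 visit becomes the Week 16 value, even one made the next day. The event date runs 31 days past the treatment end date. For someone who received the Week 12 dose it therefore falls on or after the nominal Week 16 day, and may not convert the early value to non-response.

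Sections 3.1 and 3.2.3 also conflict on whether such a value is analysed at all. If it is, nothing says whether Week 16 in the event-date comparison means the ET date, the nominal day or the end of the visit window. Two programmers could code the primary endpoint differently for the same participant, and both would be following the SAP.

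The primary non-responder imputation (NRI) analysis is affected. So are the binary key secondary endpoints, which use the same approach (Section 8.2.2), and the supportive modified composite analysis.

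**Working it through.** **Inputs**
- Day 1 is the first dose (Section 3.2.1.1), so week w is Day 7w + 1: Week 12 = Day 85, Week 16 = Day 113.
- Window ±3 days (Section 3.1): Week 12 = Days 82–88, Week 16 = Days 110–116.
- Week 12 and Week 16 are adjacent. Baseline is Visit 2 (Section 3.3) and Week 16 is Visit 8 (Section 3.5). The assessment weeks 1, 2, 4, 8 and 12 (Section 8.3.3) fill Visits 3–7.
- Four double-blind injections (Section 7), so the Week 12 dose is the last before Week 16.
- Planning rates 40% vs 15%, with 200 and 100 participants (Section 2.4.1).
- Assumption: the treatment end date is the last injection date. Section 3.4 does not say so.

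**Step 1. The plan's own figure.** Power at 40% vs 15% is 99.7% uncorrected and 99.6% with a continuity correction, in agreement with the stated >99%. It does not bear on the mapping rule but fixes the baseline for step 5.

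**Step 2. How early the value can be.** With Week 12 on Day 85, out-of-window ET days that map to Week 16 are Days 86–109. That is 109 − 86 + 1 = 24 days, from 113 − 109 = 4 to 113 − 86 = 27 days early. If Week 12 was on Day 82, the range starts at Day 83.

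**Step 3. Event date.** Event day = Week 12 dose day + 28 + 3. Dose Days 82–88 give Days 113–119; an on-time dose gives 85 + 31 = Day 116.

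**Step 4. Does the event date catch the value?** A value escapes non-response if the event day is later than the date taken as Week 16. For each dose day, out-of-window ET days run from dose day + 1 to 109, giving 27 + 26 + 25 + 24 + 23 + 22 + 21 = 168 pairs.

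| Date taken as Week 16 | Dose days that escape | Out-of-window ET pairs (of 168) | In-window ET pairs, Days 110–116 (of 49) |
|---|---|---|---|
| ET date | 82–88 for out-of-window ETs | 168 | 39 |
| Day 113 | 83–88 | 141 | 42 |
| Day 116 | 86–88 | 66 | 21 |

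These count day combinations, not participants. Doses on Days 86–88 escape on all three readings. A last dose at Week 8 (latest Day 60) gives an event day of 60 + 31 = 91, which is caught if Week 16 means Day 113 or Day 116.

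**Step 5. Size.** The SAP gives no count of such leavers.
- Each one moves the response rate by 1/200 = 0.5 points (bimekizumab) or 1/100 = 1.0 point (placebo).
- Unadjusted odds ratio at 80/200 vs 15/100: (80/120)/(15/85) = 3.78. With one bimekizumab responder reclassified as a non-responder: (79/121)/(15/85) = 3.70. With four: (76/124)/(15/85) = 3.47.
- The unadjusted Wald p-value first reaches 0.05 or more at 49/200 vs 15/100 (p = 0.061), that is, after 31 bimekizumab and no placebo reclassifications.
- ASAS-PR (17% vs 3.3%, Section 2.4.2): from 34/200, significance is lost after 15 reclassifications against 3/100 (19/200, p = 0.054) or 12 against 4/100 (22/200, p = 0.051).
- Illustration with an assumed rate: suppose 1% to 5% of each arm were affected and responded at 40% and 15%. The difference is 25.0 points with mapping, and 24.75 to 23.75 points if these values were non-response. The odds ratio is 3.78 against 3.76 to 3.69.

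**The case against.** The strongest counter-argument concerns the estimand. A reader might infer that counting someone who left on, say, Day 90 plainly violates the requirement to stay on treatment through Week 16. The documents do not support that reading. Section 8.1.2 ties the event to the Section 3.4 date, which places discontinuation where dosing cover lapses. A participant with the Week 12 dose has had all four double-blind injections, and Week 16 efficacy is assessed before the Week 16 dose (Section 3.2.2.1.2). An ET value on Days 86–109 lies within the dosing interval and is on treatment by the SAP's definition. This objection stands and narrows the point to timing and an undefined date.

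The scheduled-data sentence in Section 3.1, read literally, would keep mapped ET efficacy values out altogether. That is a fair reading, but Section 3.2.3 is more specific and Section 8.2.1.7 applies it to efficacy. The conflict is therefore part of the problem and does not answer it.

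The ±3 days is a protocol visit window, not an analysis window. No passage drops a scheduled Week 16 visit made on Day 105, so applying the window to ET data treats them more strictly. That is correct and is a cost of the fix.

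The group is also small. It is limited to people who took the Week 12 dose, left the study before Week 16, attended an ET visit and met the response there. Section 2.3 encourages those who stop the drug to keep attending.

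**Conclusion.** The point holds as a minor specification fault on the primary endpoint. Following Section 3.2.3, an assessment 4 to 27 days early (on-time Week 12 visit) can become the Week 16 value. Whether the event date then makes it non-response depends on a reference date that the SAP does not state.

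Compared with NRI of a missing Week 16, the rule can only add responders. It can do so in either arm, so it does not necessarily widen the treatment difference.

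A reader might also infer a threat to the primary conclusion. The figures do not support that: at the planning rates it would take 31 one-sided reclassifications. The expected effect is very small.

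The event days rest on the assumption that the treatment end date is the last injection date; a later CRF date would move the event date later and widen the gap. The case also requires Week 12 assessments, since without them the ET value would map to Week 12 or earlier.

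**What to change.** 1. **Section 3.2.3:** use an ET efficacy assessment as Week 16 only if it falls on Days 110–116, adopting the protocol visit window as an analysis window for ET data. Otherwise list it and treat Week 16 as missing, which Section 8.1.2 already makes non-response under NRI.
2. **Section 3.1:** name Section 3.2.3 as the governing exception for ET data.
3. **Section 3.4 or 8.1.2:** state one reference date for Week 16 in the event-date comparison whenever there is no Week 16 visit, including when an in-window ET value is used. Item 1 alone leaves 39, 42 or 21 of the 49 in-window pairs dependent on the reading. Apply the same date in the modified composite analysis, where a missing Week 16 is otherwise imputed and not set to non-response.

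**Cost:** wording changes and one date check on ET assessments. A few late leavers become non-responders, so response rates may fall slightly. In the multiple-imputation analyses, including the continuous key secondary endpoints (Section 4.2.1.6), some ET values would be imputed instead of used. ET data would follow a stricter timing rule than scheduled visits, and the SAP should say so.

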3.3 Definition of Baseline values

A Baseline value for a study participant is defined as the latest measurement for that study participant up to and including the day of administration of first study medication (ie, generally Visit 2). When no treatment information is available, the randomization date will be used as reference in place of the first day of study drug administration. If a Baseline assessment is taken on the same day as first administration of study medication, it is eligible to be used as the Baseline value, even in the case that the time of the assessment is recorded as taking place after the time of first study medication administration. This is considered acceptable as this measurement is still the best representation of the Baseline value of the given assessment since it

is highly unlikely that the study medication could have an impact on any measurement in such a short period of time. However, such cases should be rare as study center personnel are instructed to do all assessments at the Baseline visit prior to administering study medication. One exception to this rule is plasma concentration. If Baseline plasma concentration is measured at a time after the first administration of study medication, then it should not be eligible to be considered as a Baseline plasma concentration. Such cases should be discussed with the quantitative clinical pharmacologist.

For HLA-B27 only, the Baseline value may be based on a value recorded after the first study medication administration because the study medication is not expected to have any impact on the HLA-B27 measurement.

If a Baseline measurement is missing or not collected, and a Screening value is available, the Screening value will be utilized as Baseline instead. If no measurement is available prior to receiving study medication, then the Baseline value is treated as missing. Finally, re-test value can be considered to define a Baseline, as mentioned in Section 3.1.

Baseline values for component scores should be computed using components from the same visit where the relevant measurements were recorded prior to dosing. However, if the Screening visit has all of the components, but the Baseline visit is missing one or more components, the Baseline value for the component score will be calculated using the Screening visit values.

When the time of first dose is derived, it should be based on the first injection of study treatment, regardless of whether or not it is an active treatment.

For study participants randomized to placebo that switched to bimekizumab at the Week 16 visit the laboratory data (only for the shift table analyses, the analyses on TEMA and Hy's Law cases) and the vital sign data (only for the TEMA analyses) will have an additional Baseline for the Maintenance Period that will correspond to the latest measurement on or prior to the first bimekizumab dose in that period. This Baseline will be called "Baseline Week 16". To avoid any confusion in the outputs where both Baseline values will be used, the Baseline relative to the administration of first study medication will be called "Baseline Day 1".

For the MRI substudy, Baseline will also be defined as the latest measurement for that study participant up to and including the day of administration of first study medication. However, the efficacy analyses for the substudy will be performed using two sets of study participants based on the date of the Baseline MRI relative to first study medication administration: 1) all eligible substudy participants with an MRI any time prior to first study medication administration, and 2) eligible substudy participants with an MRI performed any time from 3 weeks prior to the first administration of study medication up to the day of administration of first study medication. Ideally, the Baseline MRI would be performed as close to the first administration of study medication as possible to allow accurate measurement of disease status at Baseline by SPARCC and ASpiMRI-a (Berlin modification) score. However, several factors including rescreening and cross-screening of participants, the COVID-19 pandemic, and other unforeseen issues resulted in several participant MRI scans that were >3 weeks prior to the first administration of study medication. Because there is no generally accepted window for the definition of Baseline for MRI endpoints, two sets of participants were identified to include: 1) all eligible substudy participants, and 2) only participants with MRI's performed close to the first study drug administration. The threshold of 3 weeks prior to the first study drug administration was selected after consultation with imaging experts.

For spine x-ray, the Baseline value may be based on an x-ray performed up to 6 months prior to first administration of study drug.

